7.3.8. Diabetic Dietary, Exercise, and Home Plasma Glucose Monitoring Advice

Standard diabetic dietary, exercise, and home blood glucose monitoring advice as well as on the signs and symptoms of hypoglycemia and on supplemental oral glucose treatment will be provided at Visit 1 (Week 26) and reinforced at each study site visit through the End of treatment visit (Week 52). Subjects should monitor the blood glucose as per the instructions of the investigator and as appropriate for their medical management. The subjects should report promptly, as directed by the investigator, the occurrence of hyperglycemia or hypoglycemia (particularly if symptomatic) to the investigator (or his or her designee). Assessment and action should then occur as deemed appropriate by the investigator.

7.3.9. Hypoglycemic Events

Specific criteria for monitoring hypoglycemic events have been designed to ensure subject safety and to closely monitor hypoglycemia. Hypoglycemic events are defined as follows [Seaquist, 2013]:

Severe Hypoglycemia

- Severe hypoglycemia is an event requiring assistance of another person to actively administer carbohydrates, glucagon, or take other corrective actions. Plasma glucose concentrations may not be available during an event, but neurological recovery following the return of plasma glucose to normal is considered sufficient evidence that the event was induced by a low plasma glucose concentration.

Documented Symptomatic Hypoglycemia

- Documented symptomatic hypoglycemia is an event during which typical symptoms of hypoglycemia are accompanied by a measured plasma glucose concentration ≤ 70 mg/dL (≤ 3.9 mmol/L).

Asymptomatic Hypoglycemia

- Asymptomatic hypoglycemia is an event not accompanied by typical symptoms of hypoglycemia but with a measured plasma glucose concentration ≤ 70 mg/dL (≤ 3.9 mmol/L).

Probable Symptomatic Hypoglycemia

- Probable symptomatic hypoglycemia is an event during which symptoms typical of hypoglycemia are not accompanied by a plasma glucose determination but that was presumably caused by a plasma glucose concentration ≤ 70 mg/dL (≤ 3.9 mmol/L).

Pseudohypoglycemia

- Pseudohypoglycemia is an event during which the person with diabetes reports any of the typical symptoms of hypoglycemia with a measured plasma glucose concentration > 70 mg/dL (> 3.9 mmol/L) but approaching that level.

Any hypoglycemic event, regardless of intensity, that satisfies the definition of an SAE ([Appendix 4](#)) should be categorized as outlined in this section and reported appropriately in the SAE eCRF page and the hypoglycemic events AE of special interest page.

7.4. Tracking of Albiglutide Liquid Auto-injector Failures and User Errors

All albiglutide liquid auto-injector failures and user errors must be detected, documented, and reported by the investigator throughout the study. Detailed information on auto-injector failures and user errors will be collected on the Auto-injector Failure Reporting Form.

NOTE: Albiglutide liquid auto-injector failures and user errors associated with or resulting in events fulfilling the definition of an AE or SAE will follow the processes outlined in [Section 7.3.1](#).

7.5. Immunogenicity

Serum for antidrug antibody testing will be obtained from all subjects before administration of study treatment according to the Time and Events Table in [Section 7.1](#). With exception of Week 30, all other time points (Week 26, Week 36, Week 52 and Week 60 (Follow-up)) are comparable to those collected in the Phase III Harmony studies with lyophilized albiglutide and may serve as comparators to the formulation of the marketed product.

The presence of anti-albiglutide antibodies will be assessed using a validated enzyme-linked immunosorbent assay. The assay involves screening, confirmation, and titration steps (tiered-testing approach). Confirmed positive samples will be titrated to obtain the titre of antibodies and tested for GLP-1 and albumin cross-reactivity, as well as for albiglutide neutralizing activity. Samples positive for both anti-GLP-1 antibodies and drug neutralizing antibodies may be tested for GLP-1 neutralizing activity ([Appendix 6](#)).

Additionally, in the case of severe allergic reactions that include anaphylaxis, angioedema, or other severe potential hypersensitivity reactions, three 1-mL serum samples should be obtained for immunogenicity testing (within 24 hours of the event if possible) and sent to the central laboratory (see details in the SRM) for immediate distribution to a contracted testing facility for specific immunological testing (albiglutide-specific IgE and other tests, as appropriate) A follow-up serum sample will be collected 8 weeks after the final dose of study treatment as per the Protocol Time and Events Schedule in Section 7.1.

7.6. Efficacy

HbA_{1c} and FPG will be measured at the time points specified in the Time and Events Schedule in Section 7.1. Blood samples for HbA_{1c} and FPG should be collected before administration of study treatment.

7.7. Value Evidence and Outcomes

In this open-label extension study, subjects will self-administer their medication via the auto-injector device, thereby gaining first time personal experience with its use. Subject experience with the auto-injector device and treatment will be collected via a patient self-completed exit questionnaire at the end of treatment visit (Week 52). The close-ended questionnaire focuses on elements of burden, experience and satisfaction with the auto-injector and albiglutide liquid drug product. Specifically, the questions evaluate how comfortable subjects feel about using the device, how long it took for them to feel comfortable using the device, how easy they think it is to use, how long it takes to prepare/administer and whether they prefer it to other methods for self-injection (assuming that they have prior experience) (see [Appendix 8](#) for further details)

7.8. Genetics

Information regarding genetic research is included in [Appendix 7](#)

8. DATA MANAGEMENT

For this study, subject data will be entered via an eCRF into Oracle Clinical Remote Data Capture (OC RDC) system. Subject data will be available for viewing through access to the OC RDC system. Data provided from other sources will be received, reconciled, combined and transferred to GSK at predetermined time points.

Management of clinical data will be performed in accordance with applicable PPD standards and data cleaning procedures to ensure the integrity and quality of the data, e.g., removing errors and inconsistencies in the data. Adverse events and concomitant medication terms will be coded using the Medical Dictionary for Regulatory Activities (MedDRA) and a validated medication dictionary GSKDrug.

The eCRFs (including queries and audit trails) will be sent at the end of the study in CD format to GSK to be retained. Each investigator will receive a copy of their site specific data in the same format to maintain as the investigator copy. In all cases, subject initials will not be collected or transmitted.

9. STATISTICAL CONSIDERATIONS AND DATA ANALYSES

9.1. Hypotheses

This open label study is designed to evaluate the extended safety and tolerability as assessed by immunogenicity of albiglutide liquid drug product when used in subjects with T2DM for additional 26 weeks. The overall general safety and tolerability of albiglutide liquid drug product will be assessed by reporting descriptive statistics.

9.2. Sample Size Considerations

The total number of subjects for this study will be determined by the number of subjects who give consents to enroll in this study from the parent Study 200952, have completed Study 200952, and satisfy all inclusion/exclusion criteria. Therefore, it is anticipated to enroll a maximum of 300 eligible subjects who will receive albiglutide liquid drug product.

9.2.1. Sample Size Assumptions

No sample size assumptions are planned for this study.

9.2.2. Sample Size Sensitivity

No sample size sensitivity is planned for this study.

9.2.3. Sample Size Re-estimation or Adjustment

No sample size re-estimation is planned for this study.

9.3. Data Analysis Considerations

9.3.1. Analysis Populations

Safety Population: The Safety Population is defined as all enrolled subjects who receive at least 1 dose of study medication.

Intent-to-Treat (ITT) Population: The ITT Population will include all subjects who receive at least 1 dose of the study medication and have a baseline assessment.

Other analysis populations may be defined in the reporting and analysis plan (RAP).

9.3.2. Interim Analysis

No interim analysis is planned for this study.

9.4. Key Elements of Analysis Plan

9.4.1. Primary Analyses

The overall general safety and tolerability of albiglutide liquid drug product will be evaluated in tabular and/or graphical format and summarized descriptively.

AEs and SAEs, physical examinations, clinical laboratory evaluations, vital sign measurements, and 12-lead electrocardiogram will be summarized. For continuous variables, these summaries will include sample size, mean, median, standard deviation (and/or standard error), minimum, and maximum. For categorical variables, the summaries will include frequencies and corresponding percentages. The exposure-adjusted incidence rate will also be calculated as the number of events in a given period divided by the total person time on treatment of subjects at risk within the same period. The exposure-adjusted incidence rate will be expressed as an annualized rate expected. No inferential testing will be performed on the safety variables. Hypoglycemic events will be analyzed separately from other AEs. All hypoglycemic events will be classified as severe, documented symptomatic, asymptomatic, probable symptomatic, and pseudohypoglycemia, as defined in Section [7.3.9](#).

AEs will be coded using MedDRA. AEs will be summarized in various subsets, including on therapy AEs, related AEs, AEs leading to treatment discontinuation or withdrawal from study, SAEs, fatal AEs, etc. AEs will also be summarized by maximum intensity (mild, moderate, and severe).

The evaluation of the safety and tolerability as assessed by immunogenicity of albiglutide liquid drug product will be provided by reporting descriptive statistics.

Anti-albiglutide antibody results will be summarized. In addition, the number and percentage of subjects with positive results along with the antibody titer values will be provided by visit.

Summary data for the primary analyses will be presented by visit and by subjects who needed hyperglycemic rescue during Study 200952 (at visit 1 of the current study), by subjects who did not need hyperglycaemic rescue during study 200952, and overall.

9.4.2. Exploratory Analyses

The overall general safety and tolerability of albiglutide liquid drug product as assessed by AEs and SAEs, physical examinations, clinical laboratory evaluations, vital sign measurements, and 12-lead ECGs for subjects who are randomized to albiglutide lyophilized in Study 200952 and transition to albiglutide liquid drug product in this extension study will be summarized analogous to the data in Section [9.4.1](#).

The safety and tolerability as assessed by immunogenicity for the subjects who transition to albiglutide liquid drug product in this extension study will be summarized descriptively.

The exploratory endpoints change from baseline for HbA_{1c} and FPG at week 52 for those subjects who transition to albiglutide liquid product will be presented in tabular and/or graphical format and summarized descriptively together with the 95% CI.

Patient experience and satisfaction will be assessed using descriptive summary statistics of individual questions of the 9-item questionnaire ([Appendix 8](#)).

Summary data for the exploratory analyses will be presented by subjects who needed hyperglycemic rescue during Study 200952 (at Visit 1 of the current study), by subjects who did not need hyperglycaemic rescue during study 200952, and overall.

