1. PROTOCOL SYNOPSIS FOR STUDY 204682

Rationale

Albiglutide is a novel analogue of glucagon-like peptide-1 (GLP-1) with a sufficiently long half-life to permit once a week injection. Albiglutide has been developed for the treatment of type 2 diabetes mellitus (T2DM) as an adjunct to diet and exercise, as monotherapy, or in combination with existing therapies and has been approved by the US Food and Drug Administration (FDA), the European Medicines Agency (EMA) and other regulatory agencies.

This open-label extension (Study 204682) to Study 200952 will provide additional safety, tolerability and immunogenicity data for the albiglutide liquid drug product.

Objective(s)/Endpoint(s)

Primary	

 To provide extended safety, tolerability and immunogenicity data for the albiglutide liquid drug product. 	
 Adverse events (AEs) and serious adverse events (SAEs), physical examinations, clinical laboratory evaluations, vital signs, and 12-lead electrocardiograms (ECGs). Anti-albiglutide antibody production over time.
Exploratory	

 To provide safety and tolerability data on the transition from albiglutide lyophilized to liquid drug product. To further evaluate the PD effect of albiglutide liquid drug product on HbA1c and FPG. To gain additional patient experience with the albiglutide liquid drug product via auto-injector. 	
 AEs and SAEs, physical examinations, clinical laboratory evaluations, vital signs, and 12-lead ECGs. Anti-albiglutide antibody production over time. Change from baseline in HbA1c and FPG at Week 52. Exploring patient experience and satisfaction.

Overall Design

- This is a 26 week, open-label, single group, multicenter, extension study to Study 200952. This extension study will provide extended safety, tolerability and immunogenicity data for the albiglutide liquid drug product.
- This extension study will recruit subjects who have completed Study 200952 and satisfy all inclusion/exclusion criteria.

- In addition to receiving albiglutide liquid drug product, subjects will continue on their current regimen of diet and exercise or stable dose of background metformin (if applicable).

Treatment Arms and Duration

- This extension study will comprise 2 study periods: treatment (26 weeks) and post-treatment follow-up (8 weeks).
- All subjects will receive 50 mg albiglutide liquid drug product via auto-injector.

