- Study treatment will be administered once weekly by s.c. injection in the abdomen, thigh, or upper arm.

Type and Number of Subjects

- This extension study will recruit subjects who have completed Study 200952 and satisfy all inclusion/exclusion criteria.
- A maximum of 300 subjects will be eligible to take part in this extension study.

Analysis

Primary analyses:

The overall general safety and tolerability of albiglutide liquid drug product will be evaluated in tabular and/or graphical format and summarized descriptively.

The evaluation of the safety and tolerability as assessed by immunogenicity of albiglutide liquid drug product will be provided by reporting descriptive statistics.

Exploratory analyses:

The overall general safety and tolerability of albiglutide liquid drug product for subjects who are randomized to albiglutide lyophilized drug product in Study 200952 and transition to albiglutide liquid drug product in this extension study will be evaluated in tabular and/or graphical format and summarized descriptively.

The safety and tolerability as assessed by immunogenicity for the subject who transition to albiglutide liquid drug product in the extension study will be summarized descriptively.

HbA1c and FPG change from baseline will be summarized descriptively and/or graphically.

Patient experience and satisfaction with the auto-injector and albiglutide liquid product as measured by a self completed patient exit questionnaire at the end of treatment visit (Week 52) will be assessed using summary statistics.

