3. OBJECTIVE(S) AND ENDPOINT(S)

Objectives	Endpoints
Primary	

 To provide extended safety, tolerability and immunogenicity data for the albiglutide liquid drug product. 	
 AEs and SAEs, physical examinations, clinical laboratory evaluations, vital signs, and 12-lead ECGs. Anti-albiglutide antibody production over time.
Exploratory	

 To provide safety and tolerability data on the transition from albiglutide lyophilized to liquid drug product. To further evaluate the PD effect of albiglutide liquid drug product on HbA_{1c} and FPG. To gain additional patient experience with the albiglutide liquid drug product via auto-injector. 	
 AEs and SAEs, physical examinations, clinical laboratory evaluations, vital signs, and 12-lead ECGs. Anti-albiglutide antibody production over time. Change from baseline in HbA_{1c} and FPG at Week 52. Exploring patient experience and satisfaction.

[figure not shown]

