9.4.3. Other Analyses

No other analyses will be conducted for this study.

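### Section 9.4.2 limits the Week 52 HbA1c and FPG change, with its 95% CI, to transitioning subjects; the objective, endpoint and synopsis carry no such limit

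*Protocol*

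**What the plan says.** Section 3 and the synopsis give a pharmacodynamic objective for the liquid product: "To further evaluate the PD effect of albiglutide liquid drug product on HbA1c and FPG". The endpoint in Section 3 is "Change from baseline in HbA_{1c} and FPG at Week 52". Neither names a subgroup.

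The synopsis, under exploratory analyses, states: "HbA1c and FPG change from baseline will be summarized descriptively and/or graphically". Again there is no subgroup.

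Section 9.4.2 plans the same endpoint differently. The change from baseline in HbA1c "and FPG at week 52 for those subjects who transition to albiglutide liquid product will be presented in tabular and/or graphical format", and the same sentence attaches the 95% CI.

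Section 9.4.3 then closes the list: "No other analyses will be conducted for this study".

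**The concern.** One named endpoint has two different populations. The objective, the endpoint and the synopsis point to everyone treated with liquid product; Section 9.4.2 points to those who transition to it. If *transition* means moving from lyophilized to liquid, subjects already on liquid in Study 200952 drop out of the planned summary and its interval.

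They are the subjects with the longest exposure to the product that the objective names. Followed as written, the endpoint would describe only subjects with 26 weeks on liquid. Two analysts working from the same protocol could also build the table on different populations and each cite the text in support.

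**Working it through.** The protocol states no sample size, precision or power figure for this endpoint, so there is no figure to reproduce. The check is a comparison of texts, followed by simple counts.

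**Step 1. What *transition* means in this protocol.**
- Section 3, a separate exploratory objective: "To provide safety and tolerability data on the transition from albiglutide lyophilized to liquid drug product".
- Section 9.4.2, first paragraph, on safety: "for subjects who are randomized to albiglutide lyophilized in Study 200952 and transition to albiglutide liquid drug product in this extension study".
- Synopsis, on safety: "for subjects who are randomized to albiglutide lyophilized drug product in Study 200952 and transition to albiglutide liquid drug product in this extension study".

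All three tie the word to a move from lyophilized to liquid. Section 2.1 says the parent study compares the two products, so subjects randomized to liquid there have no other product to move from.

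**Step 2. Synopsis against Section 9.4.2.** Both list these three exploratory analyses in the same order.

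| Analysis | Synopsis | Section 9.4.2 |
|---|---|---|
| General safety and tolerability | Lyophilized-to-liquid subjects | Lyophilized-to-liquid subjects |
| Immunogenicity | Transitioning subjects | Transitioning subjects |
| HbA1c and FPG change | No limit; no CI mentioned | Transitioning subjects; 95% CI |

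The limit differs only in the third row.

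**Step 3. Whether another planned analysis covers the omitted subjects.** Table 4 in Section 7.3.6 lists HbA1c and FPG, and Section 9.4.1 summarizes laboratory data by visit, by rescue status in Study 200952, and overall. Values for liquid-to-liquid subjects may therefore appear there. But Section 9.4.1 promises neither change from baseline nor a CI for them, and rescue status is the only subgroup split it names, so they would be pooled with switchers.

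**Step 4. Exposure to liquid product.**
- Liquid in both studies: 26 weeks (parent treatment phase, Section 5.1) + 26 weeks (extension, Section 4.2) = 52 weeks.
- Lyophilized, then liquid: 0 + 26 = 26 weeks.

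**Step 5. Data available.** The Time and Events Table in Section 7.1 marks both HbA1c and FPG at Weeks 26, 30, 36, 42, 48, 52 and 60: 7 of 7 visits, for all subjects.

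**Step 6. Number of subjects outside the summary.** The maximum is 300 (Sections 4.3 and 9.2). The parent allocation is not in the document, so the liquid share is assumed:
- 300 × 1/3 = 100
- 300 × 1/2 = 150
- 300 × 2/3 = 200

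**The case against.** - **Everyone transitions.** The HbA1c and FPG sentence does not repeat the clause about randomization to lyophilized product. Section 7.7 describes use of the auto-injector as a first experience for subjects, so in that respect all of them change something at Visit 1. This reading is possible. But it gives the word a second meaning within one section, and a phrase that selects some subjects would then exclude nobody. If both readings are open, the sentence still needs fixing.
- **The word *overall* at the end of Section 9.4.2 restores everyone.** It pools the rescue strata from the parent study. It does not mention parent-study product and does not clearly lift the limit.
- **The laboratory summaries already report these subjects.** This stands in part: their values are not lost, and Section 9.4.3 does not cancel Section 9.4.1. What is missing is the named endpoint, that is, the change score with its interval.
- **The 52-week argument depends on which baseline is meant.** This is fair as a limit on interpretation. With a Week 26 baseline, the change in liquid-to-liquid subjects would cover only Weeks 26 to 52. The exposure count is still correct, and the group is left out whichever baseline applies. The choice of baseline is not part of this point.
- **The counts rest on assumptions.** They do: 300 is a cap and the shares are assumed. They show scale only.
- **The analysis plan will settle it.** It may, but it would have to depart either from Section 9.4.2 or from the objective and synopsis. The protocol states a rule here; it does not leave one open.
- **Table columns and a synopsis without the CI are ordinary matters.** The missing CI alone would not be worth raising. The difference in population is.

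**Conclusion.** The point holds. Read as its own usage suggests, Section 9.4.2 gives a summary narrower than the objective and endpoint it serves, and it disagrees with the synopsis. Subjects on liquid product in both studies are left out of the Week 52 change from baseline and its 95% CI: 100, 150 or 200 of at most 300, under assumed liquid shares of 1/3, 1/2 or 2/3.

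Confidence is medium, because the looser reading of *transition* cannot be ruled out. The consequence is limited: the endpoint is exploratory and descriptive, no test or power figure depends on it, and the primary safety and immunogenicity analyses are unaffected. It should be corrected, but it does not threaten the study's main purpose.

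**What to change.** Reword the HbA1c and FPG sentence in Section 9.4.2 so that the Week 52 change from baseline is summarized with its 95% CI for the ITT Population defined in Section 9.3.1, overall and by parent-study product (liquid-to-liquid and lyophilized-to-liquid). Keep the existing presentation by rescue status. Use the same sentence in the synopsis.

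If the limit to switchers was intended, the objective, endpoint and synopsis would instead have to state it. That would leave the subjects with the longest liquid exposure unreported for this endpoint.

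The cost is one sentence in Section 9.4.2, one in the synopsis and a few more table columns. No new data are needed.

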5.3. Hyperglycemia Rescue

During the study of diabetics, there is always the possibility of hyperglycemia which might impact subject safety. Subjects who experience persistent hyperglycemia will qualify to undergo hyperglycemia rescue. Investigators must adhere to the labeling of the US FDA-approved prescribing information or to the local labeling of the respective country for all rescue medications. The conditions for hyperglycemia rescue are defined in [Table 3](#).

Table 3 Conditions for Hyperglycemia Rescue

Time Interval on Treatment	Hyperglycemia Rescue
≥Week 26 and <Week 52	HbA _{1c} ≥8.5%

1. HbA_{1c} = glycosylated hemoglobin

Subjects can be rescued at any time. Subjects who qualify for rescue should return to the study center for a rescue visit, which includes efficacy assessments. The laboratory assessments should include safety laboratory tests (e.g., chemistry and complete blood count) and HbA_{1c}. As determined by the investigator, rescued subjects may be seen more frequently during unscheduled visits until their diabetes has stabilized. Subjects will continue in the study after rescue and will continue with their blinded study treatment until the study is completed. It is critical that subjects continue in the study after rescue in order to have complete and unbiased follow-up of long-term safety and efficacy assessments.

The rescue and uptitration criteria above should apply in the majority of circumstances; however, in the event a subject experiences significant evidence of hyperglycemia (e.g., symptoms of polyuria and polydipsia and laboratory evidence of hyperglycemia), the investigator may, based upon his or her judgment, rescue the subject with appropriate therapy at any time following randomization. Such subjects may either have rescue medication added to the existing randomly assigned study medication or, if in the judgment of the investigator (or the product labeling for rescue medications) this is not appropriate, the subject will be discontinued from study medication and appropriate rescue therapy initiated. Such subjects will continue to be followed in the study for their cardiovascular and other safety information; however, they will not receive further study medication. Rather they will be prescribed alternative therapy in order to optimize their diabetes control.

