12. Follow-up visit for subjects who have discontinued study treatment (see Section 5.4) or subjects who have completed the 52 week treatment period.
13. Visit 1 of 204682 is also the end of treatment visit in Study 200952.
14. Visit 1 of Study 204682; albiglutide liquid drug product administered to all study subjects.

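### The rescue grouping in Sections 9.4.1 and 9.4.2 refers to the parent study, so no stated summary shows rescue first given during the extension

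*Protocol*

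**What the plan says.** **Grouping.** Section 9.4.2 states: "Summary data for the exploratory analyses will be presented by subjects who needed hyperglycemic rescue during Study 200952". Section 9.4.1 sets the same grouping for the primary safety summaries and completes it with "by subjects who did not need hyperglycaemic rescue during study 200952, and overall". Both sections tie rescue status to Visit 1 of the extension. Footnote 13 of the Time and Events Table (Section 7.1) adds that "Visit 1 of 204682 is also the end of treatment visit in Study 200952".

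**Event rates.** Section 9.4.1 defines an exposure-adjusted incidence rate for the safety summaries. Its denominator is the "total person time on treatment of subjects at risk within the same period". The section then says that hypoglycemic events are analysed apart from other adverse events and classified by type.

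**Rescue in the extension.** Section 5.3 states: "Subjects who experience persistent hyperglycemia will qualify to undergo hyperglycemia rescue". Table 3 gives an HbA1c criterion of 8.5% or more for Week 26 to before Week 52. Insulin is the preferred add-on. The general rule is: "Subjects will continue in the study after rescue and will continue with their blinded study treatment until the study is completed". The word for blinding does not fit an open-label study, but the interval in Table 3 places the rule in the extension. In the alternative case, where adding rescue to study drug is judged unsuitable, "the subject will be discontinued from study medication and appropriate rescue therapy initiated".

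**Rest of the analysis section.** Section 9.4.3 reads: "No other analyses will be conducted for this study". Section 9.3.1 leaves further analysis populations to the reporting and analysis plan. It does not mention data after rescue.

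**The concern.** The protocol treats rescue as important enough to split every summary by it, but the split looks back to the parent study. It is settled at the visit where the extension begins. A subject who needed no rescue in Study 200952 and starts insulin at Week 36 stays in the row for subjects not rescued in that study, and in the overall row. The label is true, but it says nothing about rescue during the period being reported.

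Two outputs are exposed:

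- **Week 52 HbA1c and FPG.** Section 3 gives the aim as the pharmacodynamic effect of the liquid product. A Week 52 value taken after rescue also carries the effect of the rescue drug.
- **Hypoglycemia.** Section 4.6.2 itself says that clinically relevant hypoglycemia with albiglutide was seen only in combination with a sulfonylurea or insulin. Insulin is the preferred rescue agent, and person-time on treatment does not stop at rescue.

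There is no control arm against which to judge the rescue component. A reader of the planned tables could not tell how much of either result follows rescue.

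**Working it through.** **1. The text.** The protocol states no figure on this point, so there is none to reproduce. Placing the sections together:

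- Status is fixed at Visit 1 (9.4.1, 9.4.2, footnote 13 of 7.1).
- Rescue can start after Visit 1, and study drug normally continues (5.3).
- By-visit displays, adverse event subsets and the lyophilized-to-liquid transition subset are also planned (9.4.1, 9.4.2). None identifies extension rescue.
- The rate wording refers to a given period, but no section ties a period to rescue.

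Blending is therefore possible in the summaries as written.

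**2. Simple mixing arithmetic.** All inputs here are assumed.

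HbA1c: shift in mean change = −(share rescued) × (extra fall due to rescue).

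| Share rescued | Extra fall 0.5 | Extra fall 1.5 |
|---|---|---|
| 5% | −0.025 | −0.075 |
| 10% | −0.05 | −0.15 |
| 20% | −0.10 | −0.30 |

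Hypoglycemia: pooled rate ÷ pre-rescue rate = 1 + f(k − 1). Here f is the share of on-treatment person-time after rescue and k is the post- to pre-rescue rate ratio. With rescue at mid-treatment on average, f is half the share rescued.

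| Share rescued | f | k = 3 | k = 10 |
|---|---|---|---|
| 5% | 0.025 | 1.05 | 1.23 |
| 10% | 0.05 | 1.10 | 1.45 |
| 20% | 0.10 | 1.20 | 1.90 |

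**3. Simulation using the protocol's threshold and visits.** The 8.5% criterion and the visits at Weeks 26, 30, 36, 42, 48 and 52 come from the protocol. The other inputs are assumed:

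- Week 26 mean HbA1c 7.0, 7.3 or 7.6; between-subject SD 0.9.
- Within-subject SD 0.45, with correlation 0.7 per 6 weeks.
- Drift 0 or +0.3 over 26 weeks.
- Rescue effect 0.5, 1.0 or 1.5 points, building linearly over 12 weeks.
- Subjects at or above 8.5% at Week 26 left out, because the parent stratum may already hold some of them.
- All rescued subjects stay on study drug.

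This gives 3 × 2 × 3 = 18 scenarios. Section 5.3 speaks of persistent hyperglycemia while Table 3 gives a single threshold, so two readings were run. Bias is measured against the same subjects' change without the rescue effect.

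| | One value ≥8.5% | Two consecutive values |
|---|---|---|
| Subjects rescued | about 5–18% | about 2–10% |
| Person-time after rescue | 3.0–9.4% | 1.0–3.7% |
| Bias in mean HbA1c change | −0.02 to −0.22 | −0.01 to −0.10 |
| Median bias | about −0.07 | about −0.03 |

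Rate inflation with k from 3 to 10:

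- One value: 1 + 0.0297 × 2 = 1.06 to 1 + 0.0944 × 9 = 1.85.
- Two values: 1 + 0.0096 × 2 = 1.02 to 1 + 0.0368 × 9 = 1.33.

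**4. Scale.** The 95% half-width is 1.96 × SD/√n. With an assumed SD of 0.8 it is 0.128 at n = 150 and 0.091 at the cap of 300. At n = 150 the bias exceeds it in 4 of 18 scenarios under one value and 0 of 18 under two. At n = 300 the counts are 8 and 1.

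**5. Supplementary summary.** In the same scenarios, using the last value on or before rescue is off by +0.003 to +0.026 points. Dropping rescued subjects is off by −0.01 to −0.06. Both depend on the assumed drift.

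**The case against.** The strongest reply is that handling of post-rescue values is ordinary analysis-plan content, and that nothing the protocol states is false. An all-data summary is legitimate and matches the purpose in Section 5.3, where rescued subjects are kept in the study for complete follow-up. The data needed for a split are collected, since rescue visits include HbA1c and medication dates are recorded. The analyses are descriptive and HbA1c and FPG are exploratory.

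Much of this stands. It also rules out several stronger readings that a reader might infer:

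- *That results are split by parent-study rescue and nothing else.* Section 9.4.1 also plans displays by visit and by adverse event subset.
- *That Section 9.4.3 forbids a split at rescue.* It can be read as saying that there is no third class of analysis, and the period wording in 9.4.1 could hold such a split.
- *That the protocol commits to an exposure-adjusted hypoglycemia rate.* Section 9.4.1 defines the rate for safety generally and does not expressly apply it to hypoglycemia.
- *That the all-data result is wrong.* It is a valid summary of what happened under the regimen as used.

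What survives is narrower. The protocol is not silent on rescue. It fixes a grouping that cannot show rescue in the extension, and it defers analysis populations only. Splitting a subject's events and person-time at the start of rescue is not a population.

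**Conclusion.** The point holds in limited form. As written, the Week 52 HbA1c and FPG change and the hypoglycemia summaries, including any exposure-adjusted rate, can blend data from before and after extension rescue, and no stated summary lets a reader see how much.

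The size is unknown. The protocol gives no rescue share, rescue effect, SD or rate ratio, so every range above rests on assumed inputs. The upper figure of 1.85 needs the highest simulated person-time share, a tenfold rate ratio, and continued study drug in every rescued subject, although Section 5.3 allows stopping. Under the two-value reading the HbA1c bias never exceeds the half-width at n = 150. The effect may well be small, and the documents do not support a claim that it is large.

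The harm is to the interpretation of descriptive results; no decision rule or error rate is involved. Nor would a split isolate the product: Section 6.3 allows metformin adjustment and Section 6.10.1 allows other medication changes. This is a worthwhile low-cost improvement, not a threat to the study.

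**What to change.** Keep the parent-study split and the all-data summaries, and add the following:

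- **Section 9.4.1:** report hypoglycemic events and on-treatment person-time before and after the start of rescue first given in the extension.
- **Section 9.4.2:** beside the all-data result, give a supplementary Week 52 HbA1c and FPG summary. For subjects rescued in the extension it uses the last value on or before the start of rescue. Label it as approximate.
- **Each stratum:** give the number rescued in the extension, and how many of them continued or stopped study drug.
- **Section 9.4.3:** word it to match.

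The clinical rescue rule is unchanged.

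The cost is a few extra tables and the work of flagging rescue drugs. Section 6.10 already records drug names and dates, and Table 2 bars insulin and secretagogues outside rescue, which makes those easy to identify. Other agents chosen by the investigator will need a check. The supplementary summary has its own limit: it carries forward a value taken around the time of rescue and ignores later change, so it should not replace the all-data result.
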